4.2 Exclusion Criteria

- 201 Older than 50 years of age at migraine onset
- 202 History of cluster headache or hemiplegic migraine headache
- 203 Unable to differentiate migraine from other headaches
- 204 No therapeutic response with > 2 of the following 7 medication categories for prophylactic treatment of migraine after an adequate therapeutic trial. These medication categories are:
 - Category 1: Divalproex sodium, sodium valproate
 - Category 2: Topiramate
 - Category 3: Beta blockers (for example: atenolol, bisoprolol, metoprolol, nadolol, nebivolol, pindolol, propranolol, timolol)

- Category 4: Tricyclic antidepressants (for example: amitriptyline, nortriptyline, protriptyline)
- Category 5: Serotonin-norepinephrine reuptake inhibitors (for example: venlafaxine, desvenlafaxine, duloxetine, milnacipran)
- Category 6: Flunarizine, verapamil, lomerizine
- Category 7: Lisinopril, candesartan

No therapeutic response is defined as no reduction in headache frequency, duration, or severity after administration of the medication for at least 6 weeks at the generally-accepted therapeutic dose(s) based on the investigator's assessment.

The following scenarios do not constitute lack of therapeutic response:

- Lack of sustained response to a medication
 - Failure to tolerate a therapeutic dose
- 205 Used a prohibited medication, device or procedure within 2 months prior to the start of the baseline phase or during the baseline phase (Refer to [Section 6.7](#) for the list of these excluded treatments).
- 206 Received botulinum toxin in the head and/or neck region within 4 months prior to the start of the baseline phase or during the baseline phase
- 207 Taken the following for any indication in any month during the 2 months prior to the start of the baseline phase:
- Ergotamines or triptans on ≥ 10 days per month, or
 - Simple analgesics (nonsteroidal anti-inflammatory drugs [NSAIDs], acetaminophen) on ≥ 15 days per month, or
 - Opioid- or butalbital-containing analgesics on ≥ 4 days per month
- 208 Anticipated to require any excluded medication, device or procedure during the study (Refer to [Section 6.7](#) for the lists of these medications, devices and procedures)
- 209 Active chronic pain syndromes (such as fibromyalgia and chronic pelvic pain)

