10.1.2 Analysis Sets

The full analysis set (FAS) includes all subjects who were randomized in the study. The efficacy analysis set includes subjects in the FAS and who received at least one dose of investigational product and **had** at least one **change from baseline measurement in** monthly migraine days **during** the double-blind treatment phase. In the efficacy analysis set, subjects will be analyzed according to randomized treatment, regardless of the treatment received. The per-protocol set is a subset of the efficacy analysis set that includes subjects who completed the 24-week double-blind treatment phase with no major protocol violations. For safety endpoints, all randomized subjects who received at least one dose of investigational product (ie, safety analysis set) will be analyzed **according to the randomized treatment unless a subject has received the incorrect dose during the entire double-blind treatment phase.** The open-label analysis set (OLAS) will consist of all subjects receiving at least one dose of AMG 334 in the **OLTP**. This analysis set will be used when summarizing data collected during the **OLTP**.

All subjects enrolled in the CHU substudy will be included in the CHU substudy analysis set.

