6.1 Definition of Terms Included in Study Endpoints

6.1.1 Efficacy Endpoints

The baseline period for efficacy analysis is defined as the period between week -4 visit (when eDiary device is set up or eDiary device assignment date) and the day prior to study day 1 (study day 1 is not included).

Migraine Day

Any calendar day in which the subject experiences a qualified migraine headache (onset, continuation or recurrence of the migraine headache). A qualified migraine headache is defined as a migraine with or without aura, lasting for ≥ 30 minutes, and meeting at least one of the following criteria (a and/or b):

a) ≥ 2 of the following pain features:

- Unilateral
- Throbbing
- Moderate to severe
- Exacerbated with exercise/physical activity

b) ≥ 1 of the following associated symptoms:

- Nausea and/or vomiting
- Photophobia and phonophobia

If the subject took a migraine-specific medication (ie, triptan or ergotamine) during aura or to treat headache on a calendar day, then it will be counted as a migraine day regardless of the duration and pain features/associated symptoms.

Monthly Migraine Days

Number of migraine days between each monthly IP dose. Monthly migraine days at baseline is the number of migraine days in the baseline period. Days without eDiary data in each monthly interval are handled by proration according to [Section 9.3](#).

Headache Day

Any calendar day in which the subject experiences a qualified migraine or non-migraine headache (initial onset, continuation or recurrence of the headache). A qualified headache is defined as:

- a qualified migraine headache (including an aura-only event that is treated with acute migraine-specific medication), or
- a qualified non-migraine headache, which is a headache that lasts ≥ 30 minutes and is not a qualified migraine headache, or
- a headache of any duration for which acute headache treatment is administered.

Monthly Headache Days

Number of headache days between each monthly IP dose. Monthly headache days at baseline is the number of headache days in baseline period. Days without eDiary data in each monthly interval are handled by proration according to [Section 9.3](#).

Migraine Attack

An episode of any qualified migraine headache or migraine specific medication intakes for aura only. The following rules will be used to distinguish an attack of long duration from two attacks, or to distinguish between attacks and relapses:

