7.5 Per Protocol Set

The Per Protocol Set is a subset of the Efficacy Analysis Set which consists of subjects who received IP at Week 12, 16, and 20 and do not satisfy any of the following conditions:

- 1) Important protocol deviations that will potentially impact primary analysis of efficacy endpoints from week 16 to week 24 or violate GCP at site as specified in the IPD List ([Cabinets/AMG 334/TMF/20120309 - Episodic Migraine Prophylaxis](#))

Japan/Study Protocol Compliance/Protocol Deviation Listing) to be applied in per protocol analysis:

- Informed Consent was not provided
 - Monthly migraine days at baseline is < 4 or \geq 15
 - Monthly headache days at baseline is \geq 15
 - No therapeutic response with > 2 of the 7 medication categories for prophylactic treatment of migraine after an adequate therapeutic trial
 - Received botulinum toxin in the head and/or neck region within 4 months prior to the start of the baseline phase and throughout the study
 - Ergotamine-derivatives, steroids, and triptans used for migraine prophylaxis are excluded within 2 months prior to the start of the baseline phase and throughout the study
 - Devices and procedures used for migraine prophylaxis are excluded within 2 months prior to the start of the baseline phase and throughout the study
 - Using opioid- or butalbital-containing analgesics on \geq 4 days in any month during the 2 months prior to the start of the baseline phase
 - History of chronic pain syndromes (eg, fibromyalgia, chronic back pain, chronic pelvic pain)
 - Received current migraine prophylaxis medication prior to the start of the baseline phase after closure of the stratum
 - Received less than 75% or more than 125% of planned total dose of AMG 334 at any of the weeks 12, 16, 20 (based on unblinded information)
(Example: subject who was randomized to AMG 334 70 mg treatment group received 140 mg, not 70 mg at week 20)
 - Important GCP violation resulting in that data can't be used for analysis
- 2) In addition to above protocol deviations, subjects who did not have an observed monthly migraine day value at any of the weeks 16, 20, 24 will also be excluded from Per Protocol Set

The Per Protocol Set will be used to perform the sensitivity analysis on the primary and secondary efficacy endpoints.

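### The per-protocol list in SAP 7.5 applies only the opioid/butalbital limb of exclusion 207 and, without giving a reason, omits the triptan/ergotamine and simple-analgesic limbs

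*SAP*

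**What the plan says.** Protocol 4.2, exclusion 207, is one criterion with a common lead-in, "Taken the following for any indication in any month during the 2 months prior to the start of the baseline phase", and three alternatives:

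- the first limb, on migraine-specific drugs, reads "Ergotamines or triptans on ≥ 10 days per month, or"
- the second covers NSAIDs and acetaminophen, with its limit set at 15 days a month
- the third limb reads "Opioid- or butalbital-containing analgesics on ≥ 4 days per month"

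SAP 7.5 lists the deviations that take a subject out of the Per Protocol Set. They are described as those that could affect the primary analysis of the efficacy endpoints from Week 16 to Week 24, or that breach GCP. The list includes "Using opioid- or butalbital-containing analgesics on" 4 or more days, in any month of the same 2-month window. Neither of the other two limbs appears.

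For any date on which a subject uses a triptan or ergotamine against aura or headache, the rule in SAP 6.1.1 is: "then it will be counted as a migraine day regardless of the duration and pain features/associated symptoms". Protocol 10.1.1.5 has the same rule.

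Protocol 10.1.2 describes the per-protocol set as subjects who "completed the 24-week double-blind treatment phase with no major protocol violations" and does not define a major violation. SAP 7.5 uses the set for sensitivity analyses of the primary and secondary efficacy endpoints. SAP Section 11 records no changes from the protocol-specified analyses.

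**The concern.** Two subjects can breach the same exclusion criterion in the same window and be treated differently. One randomised despite opioid use on 4 days in a month is removed from the Per Protocol Set. One randomised despite triptan use on 12 days in a month stays in.

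The split runs against the list's own selection rule. Triptan and ergotamine days feed the efficacy endpoints by definition. They can create migraine days, which drive the primary endpoint and the 50% responder endpoint, and they are what the acute migraine-specific medication endpoint counts. An opioid day does neither. If opioid overuse is judged relevant to efficacy, it is hard to see why triptan/ergotamine overuse is not.

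At stake is how defensible the per-protocol check is. A reader would expect it to leave out subjects who breached the medication-overuse exclusion, and as written it does so only for the opioid/butalbital limb.

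**Working it through.** The plan states no figure on this point, so the check is mainly a comparison of texts.

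**1. Limbs carried over.**

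| Limb of exclusion 207 | Limit (days per month) | In SAP 7.5? |
|---|---|---|
| Ergotamines or triptans | 10 or more | No |
| Simple analgesics | 15 or more | No |
| Opioid or butalbital | 4 or more | Yes, same limit and window |

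One of three is present and two are absent. The only SAP 7.5 bullet that names triptans and ergotamines concerns their use as prophylaxis. It mirrors item 3 of Protocol 6.7 and sets no day limit on acute use. No bullet mentions NSAIDs, acetaminophen or simple analgesics.

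**2. Which drugs the omitted limbs cover.** Protocol Table 1 lists 5 triptans, 12 entries under NSAIDs (acetaminophen included), 2 ergotamines, 2 steroids and 2 tramadol products: 5 + 12 + 2 + 2 + 2 = 23. The omitted limbs cover 5 + 12 + 2 = 19 of these. The retained limb covers the 2 tramadol entries, and no butalbital product is listed.

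**3. Link to the endpoints.** The migraine-day medication rule and the continuous secondary endpoint both concern triptans and ergotamines. Neither concerns simple analgesics. The endpoint argument therefore supports the triptan/ergotamine limb alone, and the case for the simple-analgesic limb is consistency with exclusion 207.

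**4. Whether other bullets catch the same subjects.** SAP 7.5 also removes subjects with 15 or more migraine days, or 15 or more headache days, at baseline.

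- Triptans or ergotamines: a subject using them on 10 to 14 days per month breaches 207. If that use is for headache or aura and continues into baseline, it produces 10 to 14 migraine days, which is under both caps unless other headache days are added. The gap stays open here.
- Simple analgesics: SAP 6.1.1 counts a headache of any duration treated with acute medication as a headache day. Use for headache on 15 or more days that continues into baseline therefore gives 15 or more headache days and mostly meets the headache-day bullet. The gap is narrow here.
- Both caps apply to the baseline phase, whereas 207 looks at the 2 months before it.

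**5. Cost in precision if more subjects are removed.** The documents do not say how many would be, so I assume 0% to 10% per arm. With power ≈ Φ(δ / (2.8 × √(2/n)) − 1.96) and 131 per arm, the plan's figures reproduce: 89.9% for δ = 1.12 (stated 90%) and 96.4% for δ = 1.30 (stated 96%). At n = 131 × 0.9 = 117.9 they become 86.7% and 94.6%. This shows only the scale of the cost, since other exclusions would already put the Per Protocol Set below 131 per arm.

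**The case against.** The strongest reply is that the list is selective by design. It picks deviations judged relevant to efficacy, refers to an external list of important protocol deviations that is not in these documents, and omits many other exclusions. The protocol's undefined wording on major violations does not require every exclusion to be applied. This stands as a reason why the omission could be deliberate. It does not explain why one criterion was divided so that the limb most closely tied to the endpoints is the one left out, and the SAP offers no explanation.

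The reply is also right about several stronger readings that a reader might infer.

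- *Triptan overusers necessarily have high baseline counts.* Exclusion 207 concerns the 2 months before baseline and use for any indication. Baseline counts come only from the eDiary period that starts at the week -4 visit, and the migraine-day rule covers only use for aura or headache. High baseline counts are likely but not guaranteed.
- *The results are biased.* The breach precedes randomisation, allocation is blinded, the endpoints are changes from baseline, and the model adjusts for the baseline value. The documents show no mechanism that favours an arm.
- *The day counts needed are already in the database.* This is not shown. The eDiary starts after the 207 window (Protocol 7.2.13). For acute headache drugs reported in the eDiary, the CRF holds start and stop dates of as-needed use, without individual administration dates (Protocol 7.2.16).

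**Conclusion.** The inconsistency is real and small. SAP 7.5 enforces one limb of exclusion 207 and leaves out two without a reason, and for triptans and ergotamines this conflicts with the list's stated purpose. The uncovered group is mainly subjects with 10 to 14 triptan or ergotamine days per month before baseline; for simple analgesics the headache-day cap already does most of the work.

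The effect is limited to the per-protocol sensitivity analyses of the primary and secondary endpoints. The primary analysis uses the Efficacy Analysis Set and does not change. The number of violators is not given and may be near zero, so no shift in any estimate can be calculated. The conclusion rests on the text of SAP 7.5 as it stands; the external deviation list could contain an explanation that these documents do not show. This is a cheap improvement and does not call the trial's main result into question.

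**What to change.** Before unblinding, replace the opioid-only bullet in SAP 7.5 with exclusion 207 as written in Protocol 4.2, all three limbs, and apply it to the per-protocol analyses of the primary and secondary efficacy endpoints. Identify breaches from the same eligibility-deviation source that supports the present opioid bullet, and bring the external deviation list into line. If the split is intended, state in one sentence why only the opioid/butalbital limb is considered to affect efficacy.

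The cost is one bullet and a slightly smaller Per Protocol Set.

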10.3 Important Protocol Deviations

Important Protocol Deviations (IPDs) categories are defined by the study team before the first subject's visit and updated during the IPD reviews throughout the study prior to database lock. These definitions of IPD categories, sub-category codes and descriptions will be used during the course of the study. Eligibility deviations are defined in the protocol. IPDs will be summarized by randomized treatment group and listed for DBTP and OLTP, respectively.

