10.7.1 Exposure-Response Analysis

Exposure-Response (E-R) analysis will be performed. Please refer to the E-R SSAP for additional details.

11. Changes from Protocol-specified Analyses

N/A

12. Literature Citations / References

- Fitzmaurice GM, Laird NM and Ware JH. (2004). Applied Longitudinal Analysis. New York: John Wiley and Sons.
- Breslow, N. E. and Clayton, D. G. (1993), Approximate Inference in Generalized Linear Mixed Models, *Journal of the American Statistical Association*, 88, 9–25.
- Wolfinger, R. and O'Connell, M. (1993), Generalized Linear Mixed Models: A Pseudo Likelihood Approach, *Journal of Statistical Computation and Simulation*, 4, 233–243.
- Rubin, D. B. (1987), Multiple Imputation for Nonresponse in Surveys, New York: John Wiley & Sons, Inc.
- Heinze, G. and Schemper, M. (2002), A Solution to the Problem of Separation in Logistic Regression, *Statistics in Medicine*, 2002; 21:2409–2419.
- Quade, D. (1966), Rank analysis of covariance, University of North Carolina, Institute of Statistics Mimeo Series. No. 483
- Fairclough DL1, Cella DF. Functional Assessment of Cancer Therapy (FACT-G): non-response to individual questions. *Qual Life Res*. 1996 Jun;5(3):321-9.

13. Prioritization of Analyses

The tables, listings and figures for Flash Memo of primary analysis at week 24 will be prioritized.

14. Data not Covered by This Plan

There are no plans to specifically analyze or summarize the following data points.

- ECG interval data
- PK
- CCI [REDACTED]
- CCI [REDACTED]

15. Appendices

Appendix A. Technical Detail and Supplemental Information Regarding Statistical Procedures and Programs

A1 Generalized Linear Mixed Model

Generalized mixed effects repeated measure model fits data with correlations or nonconstant variability and where the response is not necessarily normally distributed, which is also known as generalized linear mixed models (GLMM). The correlations can arise from repeated observation of the same sampling units, shared random effects in an experimental design, spatial (temporal) proximity, multivariate observations, and so on.

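### The SAP removes subjects with a history of chronic pain from the Per Protocol Set, but the protocol excludes only active chronic pain

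*SAP*

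**What the plan says.** Protocol 4.2, criterion 209, excludes subjects with "Active chronic pain syndromes (such as fibromyalgia and chronic pelvic pain".

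SAP 7.5 defines the Per Protocol Set as a subset of the Efficacy Analysis Set that "consists of subjects who received IP at Week 12, 16, and 20 and do not satisfy any of the following conditions". The first group of conditions is introduced as "Important protocol deviations that will potentially impact primary analysis of efficacy endpoints from week 16 to week 24", with a reference to an external list of important protocol deviations. One bullet in that group reads "History of chronic pain syndromes (eg, fibromyalgia, chronic back pain, chronic pelvic pain". It carries no activity qualifier and no time limit.

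Three other places bear on the point:

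- Protocol 10.1.2 describes the per-protocol set as "subjects who completed the 24-week double-blind treatment phase with no major protocol violations", within the efficacy analysis set.
- SAP 10.3 states: "Eligibility deviations are defined in the protocol".
- SAP section 11, headed "Changes from Protocol-specified Analyses", contains only the entry N/A.

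On how the set is used, SAP 7.5 says: "The Per Protocol Set will be used to perform the sensitivity analysis on the primary and secondary efficacy endpoints".

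**The concern.** A per-protocol analysis is meant to show the result in subjects who met the entry criteria and were treated and observed as planned. A rule that also removes subjects who met the entry criteria changes the population described, and it labels those subjects as deviators in the deviation summaries.

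There is a practical risk as well. A programmer working from the SAP bullet and one working from criterion 209 could build different sets from the same data, and nothing in the SAP says which source prevails. Because this is a pre-specified sensitivity analysis of the primary and secondary endpoints, its membership rule should be unambiguous before treatment codes are released.

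**Working it through.** This is mainly a comparison of texts.

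1. **The two rules.**

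| Subject | Protocol criterion 209 | SAP 7.5 bullet |
|---|---|---|
| Syndrome active at screening | Excluded | Removed |
| Syndrome resolved before screening | Eligible | Removed |
| No such syndrome ever | Eligible | Kept |

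 The rules disagree in the second row only.

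2. **Is the difference in wording meaningful?** In protocol 4.2, criteria 202 (cluster headache or hemiplegic migraine), 210 (major psychiatric disorder) and 211 (seizure disorder) are framed as *history of* the condition, where any past occurrence counts. Criterion 209 says *active*. The protocol therefore uses the two terms for different things.

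3. **Do the neighbouring SAP bullets widen their sources?** The bullets on baseline migraine days, baseline headache days, prophylactic non-response and opioid or butalbital use keep the limits of criteria 106, 107, 204 and the corresponding part of 207. The botulinum toxin bullet follows protocol 6.7. The chronic pain bullet is broader than its source.

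4. **Does another part of the plan authorise the wider rule?** Protocol 10.1.2 removes subjects for non-completion or major violations, and a resolved syndrome is neither. SAP 10.3 points back to the protocol for eligibility deviations, and the protocol defines none here. SAP section 11 declares no departure.

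5. **Could an amendment explain it?** The Amendment 2 log starts from a version dated 20 August 2015. Its listed eligibility changes concern criteria 109, 221 and 227, not 209. SAP section 1 cites Protocol 1.0 of June 16, 2015, whose wording cannot be checked here. Whatever that version said, the SAP and the current protocol disagree.

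6. **Would precision suffer?** The documents give no prevalence, so this step only illustrates scale. Inputs from protocol 10.2: differences of 1.12 (70 mg) and 1.30 (140 mg), SD 2.8, 131 subjects per arm, two-sided 0.05. Power = Φ(δ / (σ√(2/n)) − 1.96). With n = 131 the standard error is 2.8 × √(2/131) = 0.346. This gives Φ(3.237 − 1.96) = 89.9% and Φ(3.758 − 1.96) = 96.4%, which reproduces the stated 90% and 96%. With an **assumed** equal loss from each arm:

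| Assumed loss | n per arm | 70 mg | 140 mg |
|---|---|---|---|
| 1% | 129.7 | 89.6% | 96.2% |
| 3% | 127.1 | 89.0% | 95.9% |
| 5% | 124.4 | 88.4% | 95.6% |
| 10% | 117.9 | 86.7% | 94.6% |

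 The Per Protocol Set will already be smaller than 131 per arm for other reasons, so these are not predictions of its power. They show that this bullet alone would cost little precision. The issue is the definition of the set.

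**The case against.** The best defence is structural. The bullet sits beneath a lead-in about important protocol deviations as specified in an external list. On that reading a deviation must first have been recorded, and a subject with a resolved syndrome has none to record. Neighbouring bullets on prophylactic use of ergotamines, steroids, triptans and devices are rule text rather than subject-level conditions, so the whole list may be shorthand for deviation categories.

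This softens the point but does not remove it. The bullet itself names the deviation as a *history*, so a reader applying the SAP has no textual reason to restrict it to active cases. What does stand is that practice may differ from the text: if the external list is coded to criterion 209, only active cases would be flagged. The list is not available, so this cannot be settled either way.

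Two further parts of the defence stand. A past pain syndrome is a pre-randomization characteristic, so this bullet does not by itself select on response to treatment. And the gap between the protocol version that the SAP cites and the current one may be the origin of the mismatch.

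A reader might also infer that chronic back pain, named in the SAP but not in criterion 209, is a second conflict. It is not: both lists of examples are open-ended, so the extra example does not change the scope of either rule.

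**Conclusion.** The inconsistency is real and rests on *history* against *active*. As written, SAP 7.5 would remove subjects who satisfy criterion 209, and nothing else in the protocol or SAP authorises that.

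Its reach is small. It touches only the per-protocol sensitivity analyses of the primary and secondary endpoints. A reader might infer that the primary result is at risk; the documents do not support that, because SAP 7.2 and 10.5 base the primary efficacy analyses on the Efficacy Analysis Set. A reader might also infer that a countable group of eligible subjects is being dropped. That is not supported either: there is no prevalence in the documents, some such subjects would leave the set for other reasons, and actual removal depends on the unseen deviation list. The number affected is unknown and could be zero. This is a minor correction, worth making because it fixes a stated rule.

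**What to change.** Before unblinding, reword the SAP 7.5 bullet as a violation of exclusion criterion 209, using that criterion's term (active chronic pain syndromes), and align the corresponding entry in the external deviation list. If the sponsor does intend the wider rule, keep it but record and justify it in SAP section 11 as a departure from the protocol's per-protocol definition, and stop describing it as a protocol deviation.

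The cost is one line in the SAP and one list entry. It needs no new data and no change to any model or to the primary analysis.
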